### • If participant is going to ED from Northwestern Location ([name]):

- Call the building security at [contact] and inform them that Police and/or Ambulance was contacted. The security officer from the building will come to NU-CRP facility, if needed. Security should arrive to facilitate within 10 minutes and help the research personnel until Police and/or Ambulance arrive.
- A research team member must provide documentation (i.e., progress note) from the investigator to give to the police/security regarding the investigator recommendation.
- Call ED (direct crisis line is [contact]) to alert that patient is on the way and to provide withall necessary information.
- Follow up with crisis team/on call resident to give information about the patient.
- Email Principal Investigators and Thresholds Site PI to notify them that the emergency procedures took place.
- Contact Thresholds research team member so that they can reach out to the participant's clinical team for follow up.
- Coordinate with Thresholds research staff contact to follow-up with participant within 24 hours to verify they were able to access the help they needed, or follow-up with ED to verify if participant

was admitted to hospital.

• Document all activities for the study file and for correspondence with clinicians/IRB.

### • If at Threshold's Ogden location ([name]):

- Inform [name] [contact]) and/or [name] [contact]) that the police and/or an ambulance are on the way. Ensure that they know where you are in the building so that they can escort emergency personnel to you when they arrive.
- A research team member must provide documentation (i.e., progress note) from the investigator to give to the police/security regarding the investigator recommendation.
- Document which hospital participant is being taken to then contact that hospital to provide the ED staff which all necessary information.
- Follow up with crisis team/on call resident at hospital to give information about the participant
- Email Principal Investigators and Thresholds Site PI to notify them that emergency procedures took place.
- o Follow up with participant's clinical team to let them know what emergency procedures took place.
- Follow-up with participant within 24 hours to verify they were able to access the help they needed, or follow-up with ED to verify if participant was admitted to hospital.
- o Document all activities for the study file and for correspondence with clinicians/IRB.

### • If at other Thresholds Location

- Inform relevant building staff/front desk staff that the police and/or an ambulance are on the way. Ensure that they know where you are in the building so that they can escort emergency personnel to you when they arrive.
- A research team member must provide documentation (i.e., progress note) from the investigator to give to the police/emergency personnel regarding the investigator recommendation.
- Document which hospital participant is being taken to then contact that hospital to provide the ED staff which all necessary information.
- Follow up with crisis team/on call resident at hospital to give information about the participant
- Email Principal Investigators and Thresholds Site PI to notify them that emergency procedures took place.
- Follow up with participant's clinical team to let them know what emergency procedures took place.
- Follow-up with participant within 24 hours to verify they were able to access the help they needed, or follow-up with ED to verify if participant was admitted to hospital.
- Document all activities for the study file and for correspondence with clinicians/IRB.

### Withdrawal of Participants

The above noted cases regarding suicidality and symptom exacerbation are the anticipated situations when the participant will be withdrawn without their consent.

Participants withdrawn from research will:

- not be called to participate in future research visits for the current study;
- have their data included in all analyses unless there is a formal, written request by the participant to have their data removed from analyses (as noted in the consent form).

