# D. 6. Visit 10 (Post-test Visit completed at Northwestern University, at a Threshold's Odgen location, or via a phone call or video-conference) will be a repeat of the following measures (see D.2. and D.3. for more details):

- 1. Brief Psychiatric Rating Scale (BPRS)
- 2. Beck Depression Inventory (BDI)
  - a. Columbia-Suicide Severity Rating Scale (C-SSRS) if triggered by BDI scores
- 3. Job-Interview Role Plays
- 4. Social Skills Performance Assessment(SSPA)
- 5. Employment History Interview (follow-up version)
- 6. Job Interview Self-Efficacy
- 7. Personal Report of Job Interview Anxiety
- 8. Intrinsic Motivation Inventory
- 9. Technology Comfort Level Questionnaire is a 6-item measure that assesses one's comfort level with computer technology (approximately 5 minutes).

In addition, VR trainees will complete the 5 item Training Experience Questionnaire (TEQ; < 5 minutes). The

Posttest Visit 10 will last approximately 150 minutes or 2 hours and 30 minutes. Participants will be paid \$50.

**D. 7. Monthly Check-in Telephone Calls for Thresholds Clients (completed via telephone) will involve a brief (<10minutes) telephone survey asking about participants' potential interview or job-related activity in the past month.** These calls will be scheduled at monthly intervals after completion of post-test until the 6-Month Follow-Up (see D. 9.), for a total of 5 calls.

D. 8. Visit 11 (6-Month Follow-Up Visit completed at Northwestern University, a Threshold's Ogden location or via a phone call or video-conference) will be a repeat of the following measures (see D.2. and D.3. for more details):

- 1. Brief Psychiatric Rating Scale (BPRS)
- 2. AUDIT-SR
- 3. DAST-10
- 4. WHOQOL-BREF
- 5. SF-36
- 6. Beck Depression Inventory
  - a. Columbia-Suicide Severity Rating Scale (C-SSRS) if triggered by BDI scores
- 7. Employment History Interview (follow-up version)
- 8. Job Interview Self-Efficacy
- 9. Personal Report of Job Interview Anxiety
- 10. Intrinsic Motivation Inventory

Participants will also complete the SF-12 health questionnaire about their physical health and the Employment History Follow-up interview that will assess how many job interviews were completed, total hours worked, how many jobs were offered (and accepted), hourly wage, type of job, jobs terminated (and why).

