The 6-Month Follow-Up Visit 11 will last approximately 90 minutes or 1 hour and 30 minutes. Participants will be paid \$40. If the participant completed at least 3 of the 5 calls before the 6-Month Follow-Up visit, they will receive a \$10 bonus.

Follow-Up Visit 10 and Visit 11 scheduling protocol.

1. Study Participants' 6-month Follow-up visit (V11) will be scheduled 2-4 weeks before their due date. Scheduling will depend on the following:

a. If a participant is engaging in the monthly employment calls, their V11 will be scheduled at the time of their 5-month employment call.

b. If a participant is NOT engaging in the monthly employment calls, staff will contact the participant 4 weeks before the V11 due date. The contact process will be to use the phone to call the participant up to three times per week (only one time per day). Given that this population is difficult to reach, we will follow-up this initial phone call with an email and text message (for those participants who identified on their consent form that we can contact them by phone or emai.

2. If the study participant's V11 has not been scheduled by 2 weeks before their due date, staff will reach out to the participant's employment specialist and primary clinician for support contacting the participant.

3. If the study participant's V11 has not been scheduled by the time of their due date, staff will send a letter to the participant. The letter will explain the nature of the visit, the length of time the visit will take, and the staff person they should contact to schedule.

4. If the study participant does not respond to the letter or if their V11 is not scheduled by 6 weeks past their

due-date, staff will pull any available information from the electronic health record, and the member's study participation will end.

The same process will be used for scheduling Visit 10 as well.

Our primary method to collect Visit 10 and Visit 11 study data will be to invite participants to complete the visits at their local Thresholds location or Northwestern (as is the same for all in person study visits).

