### F. Participant Timelines

**F. 1. Thresholds Clients.** Individuals receiving mental health services at Thresholds who are enrolled in the effectiveness trial will participate in the study for a period of 9 months. Over the first month, they will complete a series of study measures and if randomized to the intervention group, this participation will include up to 10 hours of virtual reality training. After the first month, the participants randomized to the training group are

welcome to use the training as-needed, which will be monitored using their ID number. Then approximately 6 months after participants complete their post-test visit, they will be invited to complete their 6-month follow-up visit. Approximately 3 months after the 6-month visit, participants will be contacted via phone for a 9-month follow-up interview. Their participation in the study will end at this time.

After 1/3 of the effective trial participants have completed their intervention training (and before the completion of the 6 month follow-up) 20 VR trainees will be recruited to participate in a series of focus groups.

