### **12.0 Financial Compensation:**

All participants will receive compensation per visit where research assessments are collected. Potential transportation costs are included in the planned compensation payments. If a visit is not completed in full, the participant will be paid for the portions completed. These payments are approximately \$70 for Baseline Visit 1 and Pretest Visit 2/3; \$50 for Posttest Visit 10; and \$40 for 6-Month Follow-up Visit. If a participant completes 3 out of the 5 scheduled monthly calls before the 6-Month Follow-up Visit, he/she will receive an additional \$10.

If the participant completes the two additional check-in calls before the 9-month follow-up telephone call, he/she will receive an additional bonus of \$10 after the completion of the 9-month call, Thus, the total amount that can be received for the study is approximately \$250 per participant for completing research assessments. Study participants will not be paid for completing research visits 4, 5, 6, 7, 8, and 9 because they are receiving a free intervention.

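### Participants the study withdraws for suicidality or worsening symptoms have no secured employment follow-up to T3, and those withdrawn before Visit 10 have no date to follow up from

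*Combined protocol and SAP*

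**What the plan says.** Section 10.0, under Withdrawal of Participants, lets the study remove people on safety grounds: "The above noted cases regarding suicidality and symptom exacerbation are the anticipated situations when the participant will be withdrawn without their consent". Two consequences are given. Such a person will "not be called to participate in future research visits for the current study", and their data stay in every analysis unless they ask in writing for removal. Employment status after withdrawal is not mentioned.

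The contacts that collect employment are timed from the post-test (Visit 10):

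- Monthly calls (Section 4.0, D.7): "These calls will be scheduled at monthly intervals after completion of post-test until the 6-Month Follow-Up".
- The 6-month visit, Visit 11 (Section 4.0, F.1): "approximately 6 months after participants complete their post-test visit".
- Fallback (Section 4.0, scheduling protocol for Visits 10 and 11, step 4): if Visit 11 is still unscheduled six weeks after its due date, "staff will pull any available information from the electronic health record" and participation ends. The protocol adds: "The same process will be used for scheduling Visit 10 as well".

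After randomization only IPS+VR attends visits 4 to 9, the six training sessions in D.5. Section 12.0 itself classes these as research visits: "Study participants will not be paid for completing research visits 4, 5, 6, 7, 8, and 9". The scheduled suicidality check between randomization and Visit 11 falls at Visit 10, in both arms: "Columbia-Suicide Severity Rating Scale (C-SSRS) if triggered by BDI scores".

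Section 14.0 describes the study as intent-to-treat and defines H1 as getting a job between T1 and T3. On the natural reading of an awkward phrase, it scores censored people as not employed. Multiple imputation is stated for longitudinal analyses only.

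**The concern.** An intent-to-treat comparison of employment needs the outcome for everyone randomized, and in particular for people the study itself removes. Here the withdrawal rule keeps them in the analysis set but does not secure their outcome.

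The gap could also differ by arm. Section 10.0 expects problems to surface when someone arrives at, or worsens during, a research visit. Before Visit 10 only IPS+VR has such visits, and the staff who run them know the arm.

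The consequences differ by hypothesis:

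- **H1 (employment rate):** withdrawn people scored as no job pull the arm with more withdrawals downward, so any bias runs against VR.
- **H2 (interview skills at T2):** withdrawal during visits 4 to 9 also loses the post-test role-play.
- **H3 (time to job):** the same person is censored early. If worsening also lowers the chance of a job, the censoring is informative. With more of it in IPS+VR, the comparison tilts towards VR.
- **H4 (distress at T3):** the result rests on imputation for people removed for reasons related to distress.

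**Working it through.** **The plan's own figures.** Section 14.0 gives H1 80% power with 80 per arm, 10% missing, an odds ratio of 3.2 and two-sided alpha 0.0125. With 72 per arm (80 × 0.90), 25% against 51.6% (the rate an odds ratio of 3.2 implies) and a pooled-variance test of two proportions, power is 79.3%, so the figure reproduces. For H3, 20% of IPS Only find a job by T3 at hazard 0.0085. Since −ln(0.8)/0.0085 = 26.3, that hazard is per week over about 26 weeks.

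**Step 1: what follow-up remains after withdrawal.**

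- *Withdrawn after Visit 10.* The post-test date exists. The withdrawal rule does not bar the calls, and step 4 can be read to give a record pull six weeks after the Visit 11 due date. The outcome may be recovered, though no text says so.
- *Withdrawn before Visit 10.* There is no completed post-test, so there is no call schedule and no Visit 11 due date. Step 4 can run only off Visit 10, and it then ends participation.

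**Step 2: what that early record pull would see.** At the IPS Only hazard:

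- counting from the Visit 10 due date, 6 of 26 weeks: (1 − e^(−0.0085×6)) / (1 − e^(−0.0085×26)) = 0.25;
- counting from about one month earlier, 10 of 30 weeks: (1 − e^(−0.0085×10)) / (1 − e^(−0.0085×30)) = 0.36.

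**Step 3: opportunities for withdrawal after randomization.**

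| | IPS+VR | IPS Only |
|---|---|---|
| Research visits before Visit 10 | up to 6 (visits 4–9) | 0 |
| Research visits before T3 | up to 7 (visits 4–10) | 1 (Visit 10) |
| Scheduled BDI/C-SSRS checks before T3 | 1 | 1 |

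The six extra visits therefore add unscheduled detection only.

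**Step 4: size under assumed rates.** The documents give no withdrawal rate. Let q be the chance of withdrawal per visit, equal and independent across visits. The excess share withdrawn in IPS+VR is (1 − q) − (1 − q)^7. If both arms have a true employment rate of 25% and every withdrawn person is scored 0, the H1 shift is 0.25 times that share.

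| q (assumed) | Excess share | Excess of 80 | H1 shift against VR | People of 80 |
|---|---|---|---|---|
| 0.25% | 1.49% | 1.2 | 0.37 points | 0.30 |
| 0.5% | 2.95% | 2.4 | 0.74 points | 0.59 |
| 1% | 5.79% | 4.6 | 1.45 points | 1.16 |

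This is an upper bound for each q, because visits 4–9 carry no scheduled check. If detection at those visits is one tenth of that at Visit 10 (also assumed), the excess is (1 − q)(1 − (1 − q/10)^6) = 0.15%, 0.30% and 0.59%. The shift is then 0.04, 0.07 and 0.15 points.

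**Step 5: a check against earlier experience.** Section 10.0 reports no distress from the interview or role-plays in more than 150 earlier participants. For 0 of 150, the one-sided 95% upper bound is 1 − 0.05^(1/150) = 1.98%. Distress during assessment is a different event from safety withdrawal, but 1.98% extra withdrawals would be 1.6 of 80 and a shift of 0.49 points.

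**The case against.** The strongest reply is that very few people are involved. Section 3.0 excludes recent attempts and active ideation with intent. Section 10.0 knows of no adverse events caused by the training. Some VR use may be at home, so six visits is a maximum. The 10% missing-data allowance is 8 per arm, more than the worst assumed excess of 4.6. All of this supports a low rating. The allowance, however, protects power and does not remove bias.

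A second reply is that the text partly covers the case: only visits are stopped, not telephone calls, and step 4 needs no contact with the participant. That stands for people withdrawn after Visit 10. It does not help those withdrawn earlier, whose calls and Visit 11 have no starting date.

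Third, the missing anchor affects anyone who skips the post-test, and reading the Visit 10 scheduling sentence as ending follow-up is strict. Both points are fair. The problem is wider than withdrawal, but withdrawal is where the study itself causes the loss, and no text supplies another date.

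Fourth, the consent pages were not available and may address the use of records after withdrawal. That limits confidence. The DSMB's review of retention and safety does not collect the missing outcome. Stopping visits for acutely suicidal people is sound and is not disputed.

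**Conclusion.** The concern holds, as a minor point with medium confidence. Followed as written, the plan loses the T3 employment outcome of people withdrawn before Visit 10 and most naturally counts them as not employed, in a trial analysed by intention to treat. Such withdrawals can arise at research visits that only IPS+VR attends.

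Any H1 bias runs against VR and is probably well under 1.5 points. That rests on the assumed per-visit rates, a 25% employment rate in both arms, and withdrawn people being scored as no job. The effects on H2, H3 and H4 are not quantified; for H3 the direction depends on worsening also lowering the chance of a job. No loss of power is claimed.

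**What to change.** Amend Withdrawal of Participants in Section 10.0 to say that study-imposed withdrawal stops training and assessment visits only. Unless the participant withdraws consent, employment status and job start date are still obtained to T3 from the health record and, where the clinical team agrees, from the monthly calls. For anyone withdrawn before Visit 10, date the calls and the 6-month record pull from the planned Visit 10 date. The same dating rule would serve others who miss the post-test.

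In Section 14.0, report study-imposed withdrawals by arm and visit, and add an H1 sensitivity analysis that imputes outcomes still missing instead of scoring them 0.

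The cost is protocol wording, an IRB modification, and a check that the consent covers employment data from records after study-imposed withdrawal. Existing procedures are used and no visits are added. The drawback is that health-record employment data may be less complete than the interview.

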### **11.0 Potential Benefits to Participants:**

Participants randomized to the VR training group may experience an increased likelihood of receiving a job offer. This effect was observed in five efficacy studies. Across those 5 efficacy studies, approximately 50% of

VR trainees received a job offer compared to approximately 25% of study participants who received services-asusual. Participants randomized to the control group are not likely to receive a direct benefit from participating in this study.

Participants completing the focus groups or semi-structured interviews for the implementation study are not likely to receive a direct benefit from participating in this study.

### **12.0 Financial Compensation:**

All participants will receive compensation per visit where research assessments are collected. Potential transportation costs are included in the planned compensation payments. If a visit is not completed in full, the participant will be paid for the portions completed. These payments are approximately \$70 for Baseline Visit 1 and Pretest Visit 2/3; \$50 for Posttest Visit 10; and \$40 for 6-Month Follow-up Visit. If a participant completes 3 out of the 5 scheduled monthly calls before the 6-Month Follow-up Visit, he/she will receive an additional \$10.

If the participant completes the two additional check-in calls before the 9-month follow-up telephone call, he/she will receive an additional bonus of \$10 after the completion of the 9-month call, Thus, the total amount that can be received for the study is approximately \$250 per participant for completing research assessments. Study participants will not be paid for completing research visits 4, 5, 6, 7, 8, and 9 because they are receiving a free intervention.

### **13.0** Provisions to Protect the Privacy Interests of Participants:

All methods of research data collection (interviews, self-report, role-plays) will be conducted in a private office. All methods of correspondence will be secure, including telephone, voicemails, text messages, or email. Participants will provide informed consent with respect to their preferred method of communication. In addition, will will use a personal identification number (PIN) to protect participant privacy by labeling all study documents with the PIN rather than any identifying information. The use of the PIN will help keep participant enrollment confidential.

Access to protected information will be limited to the Northwestern PI, Thresholds' Site PI, NU research team members, and the Thresholds' research team members. There will be a document located on the NU servers (password protected behind firewalls) that links PINs to study participant names. The PI, Site PI, and research teams will have access to this file in order to coordinate study visits and track participant progress to complete the study.

### 14.0 Confidentiality and Data Management:

Description of Security measure to Protect Data Sources. Paper research records will be created at Thresholds, and labeled with the PIN, where participants will be consented and complete baseline measures. These records will be stored in a locked cabinet within a locked office. These records will serve as the source for electronic data entry. The first entry of the data will occur at Thresholds. Upon completion of data entry at Thresholds, the paper research records will be transferred via a locked box to the NU research team where the data will be cleaned, re-entered into the electronic database, and stored in a locked drawer in a locked room. Paper research records will also be created at NU to cover role-play and research staff for the role-play and self-report data collected at NU. The NU and Thresholds records will be merged prior to long term storage. All records will be de-identified after study completion. All paper research data data will be stored on password protected servers for a period of 7 years.

Video recordings will stored for primary access on Northwestern University password protected servers behind firewalls. The video recordings will be stored using the study PIN as a filename: IDXXXX\_video\_a.xxx. The file name designation will also be randomized from a,b,c,d, e,f to maintain blinding as to whether the video was pre-test, post-test, or follow-up.

All participant documents at Thresholds and NU will be labeled with the participant's PIN. Each page of each document will be labeled with the PIN. Documents will be organized into a study binder that is also labeled with the participant PIN. All Binders and Study Documents will be stored in locked file drawers within a locked room.

As an adjunct faculty at Northwestern University, overall PI [name] still maintains his NU netid and password. He will be able to access REDCap to download the de-identified research data in order to review the

integrity of the data. The audio/video data that is collected will be downloaded from the video camera to a NU workstation where it will be uploaded to the server. Due to his adjunct appointment at NU, [name] will still have access to the NU server and can simply move the file from the NU server to a server at UM. Both servers will be password protected with firewall protection.

Quality Assurance Measures. All participants will be recruited using strategies, documents, and text approved by the Northwestern University Feinberg School of Medicine Institutional Review Board (IRB). The research team will regularly hold meetings to discuss the effectiveness of approved recruitment strategies and if new strategies should be reviewed by the IRB and then implemented. In addition, randomly selected measures will be selected for audio-taped review. Only those subjects who have given written consent to have measures audiotaped for quality control purposes will be part of the random audio-taped reviews. The study coordinator will screen participants for eligibility using formal study forms. The PI and Site PI will regularly audit accrual to ensure that participants meet eligibility criteria and that the study enrollment is consistent with the projected enrollment targets agreed upon with NIMH. In addition, the study coordinator will audit all study files to ensure that all required study data is completed on each form, and that there is no missing data. Data will be double entered on electronic REDCap data entry forms to maintain the validity and integrity of the collected data. The first entry will take place at Thresholds by subcontracted Thresholds staff (for Thresholds-based visits) or at NU by NU project staff (for NU-based visits), while the second entry will take place at NU by NU project staff (for all visits). The REDCap system is accessible via a virtual private network that is password protected and behind firewalls. The data will be transported from Threholds to NU in a locked storage box. To protect confidentiality, all data will be numerically coded using a personal identification number (PIN), and information linking the PIN to the subject's name will be kept in a secured file cabinet and office. All audio and video files will be stored electronically on password-protected computers and communication among the staff will use PINs, not names. No information concerning data will be presented with participant names. The biostatistician and project coordinator will also perform all necessary checks and controls to ensure the reliability and validity of the data, including monitoring data collection and collection procedures, data storage, data management, and data analysis.

Data Analysis Plan for Aims 1 & 2. In this intent-to-treat study, we will collect data on 160 subjects. The biostatistician will monitor the data for distribution normality and transform abnormally distributed variables if needed. Correction for Multiple Comparisons: To minimize spurious findings, we will adjust the 3 primary tests using a false discovery rate at 0.05 (see below). Covariates: Although randomization should protect against group differences, we will covary for any between-group differences that are observed regarding demographic, cognitive, clinical and vocational history, booster sessions, and the number of completed interviews. Missing Data: We will follow the intent-to-treat principle and in longitudinal analyses we will use multiple imputation models to analyze the data in the presence of missing data. Data processing and cleaning will occur during the study, including checking for missing data and inconsistencies. All videos will be stored on the project's secure server. A Data Safety and Monitoring Board will monitor for adverse events (see 15.0 below).

**Hypothesis 1:** IPS+VR trainees will have higher employment rates than IPS Only by T3. **To test H1**, we will use multiple logistic regression and a Wald Chi-square test of the coefficient to its standard error, to compare the adjusted employment proportions in the two conditions (attained a job=1 vs. failed to attain a job or censored with a job=0, between T1 and T3). We calculated power using simulation in R, correcting for small samples and multiple testing with false discovery rate for the 4 primary tests (our power analysis is conservative, relying on Bonferroni corrections for all tests). Accounting for 10% missing, our trial that recruits 80 subjects in each arm has 80% power for a two-sided 0.05/4=.0125 level test when the OR = 3.2, with IPS+VR effectively doubling the

rate from 25% to 53% employment. Based on our earlier study where we found an OR of 8.7, or effectively tripling the employment rate from 25% to 75%, and a power of 0.99 at this magnitude of effect, we feel confident that we will have sufficient power in this study.

**Hypothesis 2:** IPS+VR trainees will have greater improvement in *job interview skills* than IPS Only by T2. **To test H2**, we will conduct a repeated measures analysis of variance (RM-ANOVA) with pre and post interview scores as the repeated measures and treatment group as the fixed factor. Based on our pilot data, we expect r=.7 between T1 and T2 scores, and an effect size of d=.67 between pre and post interview role-play scores using VR. Assuming a small-to-moderate effect within IPS Only (e.g., d=.25), our best power estimate assumes a medium effect size contrasting IPS Only with IPS+VR (d=.67-.25=.42). This effect size and correlation imply an expected 6.9% reduction in within subject error for the treatment–x-time effect. Thus, 80 subjects at .0125 level will yield 82% power to detect this effect. For the ANOVA model, 160 subjects will be sufficient to detect a reduction of within subject error of 4.7% with 80% power. Assuming a full sample effect size of d=.46 (.67+.25)/2), this reduction in error corresponds to an effect size of d=.62 for the IPS+VR group and d=.30 in the IPS only group (a difference of d=.32).

**Hypothesis 3:** IPS+VR will get jobs sooner than IPS only by T3. **To test H3**, we will use a Cox proportional (or non-proportional) hazards regression model to assess the adjusted hazard rate on time-to-employment for IPS+VR vs. IPS Only, adjusting for potential covariates (e.g., completed training trials). For a power analysis for **H3**, we assume a constant hazard rate for the distribution of time-to-employment in both groups. We also assume that a proportion of 0.20 of the subjects in the IPS Only group will find a job by T3 (that is, a hazard rate of 0.0085 for IPS Only). This analysis is estimated based on limited pilot data and log-rank power tables. Thus, 160 subjects provide 80% power for a 0.0125-level test comparing time-to-employment in the two arms to detect a hazard rate of 2.0 for IPS+VR vs. IPS Only.

**Hypothesis 4:** IPS+VR trainees will have greater reductions in psychological distress than IPS Only between T1 and T3. **To test H4**, groups will be contrasted on change via RM-ANOVA with time as a repeated measure and group as the main effect. Power analyses for RM-ANOVA focused on contrasts between T1 and T3. A correlation of r=.5 between T1 and T3 was assumed. Power was estimated for a range of relative effect sizes (d=.2 to d=.8; difference between IPS Only and IPS+VR) for RM-ANOVA time-by-treatment interaction effects. Assuming an overall reduction in distress of d=.5 (across both groups), all relative effect sizes were centered on this average (e.g., a relative difference in d=.8, corresponds to d=.9 for IPS+VR and d=.1 for IPS, averaging out to d=.5 overall). For ANOVA change contrasts of IPS only vs. IPS+VR between T1 and T3, 160 subjects will be sufficient to detect d=.50 (d=.75 vs .25) with 80% power for 0.0125-level test. ANCOVA will test for differences in T3 distress while covarying for T1 distress. Baseline differences (e.g., cognition) will be tested as covariates.

**Hypothesis 5:** IPS+VR will be more cost-effective than IPS Only. To test **H5**, we will conduct a costeffectiveness analysis (CEA) to assess the short-term cost-effectiveness of IPS+VR relative to IPS Only using a societal perspective, which includes intervention costs and client costs provided by the IPS program director. Intervention costs include variable costs (e.g., time spent by ECRs) and fixed costs (e.g., costs supporting hiring, training, and coordination). Client costs will include time using VR and travel costs. We will use standard approaches to identifying and assigning unit costs for each cost component. We will use job attainment rate as our measure of effectiveness. The main step is to calculate an incremental cost-effectiveness ratio (ICER), which is defined as the difference in total costs between the IPS+VR and IPS Only groups, divided by the between-group difference in job attainment rate. Confidence intervals will be calculated around the ICER using bootstrapping and Fieller's theorem. We will conduct sensitivity analysis by deriving cost-effectiveness acceptability curves that display the probability of IPS+VR being cost-effective at various threshold values. **Exploratory (Person-Level):** To study the generalizability of VR to social skills, we will evaluate if more VR training (i.e., number of trials) is associated with a longer job tenure (number of weeks) and enhanced social skills using linear regression; covariates will include demographic, cognitive, vocational, and training characteristics that differentiate groups. **Exploratory (System-Level):** We will explore if, as a result of VR, ESPs reallocate their interviewing hours towards building larger employer networks, completing more job applications with clients, and engaging in more hours of coaching work communication with clients.

**Hypothesis 6:** Improved interviewing skills will mediate the relationship between VR (number of completed VR trials and employment outcomes (obtaining employment). **To test H6**, we will test first for a significant IPS+VR impact on role-play scores compared to IPS alone, then check for treatment by mediator interaction, then on the product of the two coefficients with bootstrapped confidence intervals. We simulated power for this text, finding 80% power when the effect size for skills is small (effect size=0.2) and the odds for skills leading to a job is 1.8; thus we expect to have sufficient power. These older mediational models are informative but incomplete, and these will be followed by computing the *causally interpretable average natural indirect effect* under assumptions i – iv therein. We plan to conduct sensitivity analyses to the assumption of "no exposure induced mediation-outcome confounding". For the exploratory moderated mediation model, we plan to use Approach 1 of Vanderweele et al. to account for the combined mediated (indirect) effect of both the psychological changes in self-efficacy, anxiety, and role-play scores, as suggested in Corbiere et al..

**Exploratory:** To test the moderated mediation (mediated effect varies as a function of a baseline variable), we will first conduct a standard model of post-intervention anxiety/self-efficacy serving as a mediator of the relationship between VR and interviewing skills using the "product of coefficients method". Mediation tests will be based on whether the confidence interval for the product of coefficients includes zero. This approach addresses the known non-normality of the test statistic. To this standard mediation model we will include an interaction of baseline (pre-intervention) anxiety/self-efficacy to interact with VR training on post-intervention anxiety/self-efficacy. Similarly, we will include a baseline-by-intervention interaction on interviewing skills. The Johnson-Neyman approach will assess where mediation occurs as a function of baseline levels. We will test if employment outcomes mediate the relationship between interviewing skills and psychological distress at 6-month follow-up, using the same approach outlined for **H6**.

### Data Analysis Plan for Aim 3

**Overview:** We will recruit three levels of subjects for the VR process evaluation. ECRs will recruit IPS clients, while the PI, Site PI, and Thresholds IPS Director will recruit multidisciplinary staff (e.g., ECRs), and leaders (e.g., CEO). We will use both quantitative and qualitative methods of data collection and analysis.

